## 16.0 ETHICAL ASPECTS OF THE STUDY

This study will be conducted with the highest respect for the individual participants (ie, subjects) according to the protocol, the ethical principles that have their origin in the Declaration of Helsinki, and the ICH Harmonised Tripartite Guideline for GCP. Each investigator will conduct the study according to applicable local or regional regulatory requirements and align his or her conduct in accordance with the “Responsibilities of the Investigator” that are listed in [Appendix B](#). The principles of Helsinki are addressed through the protocol and through appendices containing requirements for informed consent and investigator responsibilities.

### 16.1 IRB and/or IEC Approval

IRBs and IECs must be constituted according to the applicable local requirements of each participating region. The sponsor or designee will require documentation noting all names and titles of members who make up the respective IRB or IEC. If any member of the IRB or IEC has direct participation in this study, written notification regarding his or her abstinence from voting must also be obtained.

The sponsor or designee will supply relevant documents for submission to the respective IRB or IEC for the protocol’s review and approval. This protocol, the investigator’s brochure, a copy of the ICF, and, if applicable, subject recruitment materials and/or advertisements and other documents required by all applicable laws and regulations, must be submitted to a central or local IRB or IEC for approval. The IRB’s or IEC’s written approval of the protocol and subject informed consent must be obtained and submitted to the sponsor or designee before commencement of the study (ie, before shipment of the sponsor-supplied drug or study specific screening activity). The IRB or IEC approval must refer to the study by exact protocol title, number, and version date; identify versions of other documents (eg, ICF) reviewed; and state the approval date. The sponsor will notify site once the sponsor has confirmed the adequacy of site regulatory documentation and, when applicable, the sponsor has received permission from competent authority to begin the trial. Until the site receives notification no protocol activities, including screening may occur.

Sites must adhere to all requirements stipulated by their respective IRB or IEC. This may include notification to the IRB or IEC regarding protocol amendments, updates to the ICF, recruitment materials intended for viewing by subjects, local safety reporting requirements, reports and updates regarding the ongoing review of the study at intervals specified by the respective IRB or IEC, and submission of the investigator’s final status report to IRB or IEC. All IRB and IEC approvals and relevant documentation for these items must be provided to the sponsor or its designee.

Subject incentives should not exert undue influence for participation. Payments to subjects must be approved by the IRB or IEC and sponsor.

## **16.2 Subject Information, Informed Consent, and Subject Authorization**

Written consent documents will embody the elements of informed consent as described in the Declaration of Helsinki and the ICH Guidelines for GCP and will be in accordance with all applicable laws and regulations. The ICF, subject authorization form (if applicable), and subject information sheet (if applicable) describe the planned and permitted uses, transfers, and disclosures of the subject's personal and personal health information for purposes of conducting the study. The ICF and the subject information sheet (if applicable) further explain the nature of the study, its objectives, and potential risks and benefits, as well as the date informed consent is given. The ICF will detail the requirements of the participant and the fact that he or she is free to withdraw at any time without giving a reason and without prejudice to his or her further medical care.

The investigator is responsible for the preparation, content, and IRB or IEC approval of the ICF and if applicable, the subject authorization form. The ICF, subject authorization form (if applicable), and subject information sheet (if applicable) must be approved by both the IRB or IEC and the sponsor before use.

The ICF, subject authorization form (if applicable), and subject information sheet (if applicable) must be written in a language fully comprehensible to the prospective subject. It is the responsibility of the investigator to explain the detailed elements of the ICF, subject authorization form (if applicable), and subject information sheet (if applicable) to the subject. Information should be given in both oral and written form whenever possible and in the manner deemed appropriate by the IRB or IEC. In the event the subject is not capable of rendering adequate written informed consent, then the subject's legally acceptable representative may provide such consent for the subject in accordance with applicable laws and regulations.

The subject, or the subject's legally acceptable representative, must be given ample opportunity to: (1) inquire about details of the study and (2) decide whether or not to participate in the study. If the subject, or the subject's legally acceptable representative, determines he or she will participate in the study, then the ICF and subject authorization form (if applicable) must be signed and dated by the subject, or the subject's legally acceptable representative, at the time of consent and before the subject entering into the study. The subject or the subject's legally acceptable representative should be instructed to sign using their legal names, not nicknames, using blue or black ballpoint ink. The investigator must also sign and date the ICF and subject authorization (if applicable) at the time of consent and before subject entering into the study; however, the sponsor may allow a designee of the investigator to sign to the extent permitted by applicable law.

Once signed, the original ICF, subject authorization form (if applicable), and subject information sheet (if applicable) will be stored in the investigator's site file. The investigator must document the date the subject signs the informed consent in the subject's medical record. Copies of the signed ICF, the signed subject authorization form (if applicable), and subject information sheet (if applicable) shall be given to the subject.

All revised ICFs must be reviewed and signed by relevant subjects or the relevant subject's legally acceptable representative in the same manner as the original informed consent. The date the

**CONFIDENTIAL**

revised consent was obtained should be recorded in the subject's medical record, and the subject should receive a copy of the revised ICF.

### **16.3 Subject Confidentiality**

The sponsor and designees affirm and uphold the principle of the subject's right to protection against invasion of privacy. Throughout this study, a subject's source data will only be linked to the sponsor's clinical study database or documentation via a unique identification number. As permitted by all applicable laws and regulations, limited subject attributes, such as sex, age, or date of birth, and subject initials may be used to verify the subject and accuracy of the subject's unique identification number.

To comply with ICH Guidelines for GCP and to verify compliance with this protocol, the sponsor requires the investigator to permit its monitor or designee's monitor, representatives from any regulatory authority (eg, the United States Food and Drug Administration, the United Kingdom Medicines and Healthcare products Regulatory Agency, the Pharmaceuticals and Medical Devices Agency of Japan), the sponsor's designated auditors, and the appropriate IRBs and IECs to review the subject's original medical records (source data or documents), including, but not limited to, laboratory test result reports, ECG reports, admission and discharge summaries for hospital admissions occurring during a subject's study participation, and autopsy reports. Access to a subject's original medical records requires the specific authorization of the subject as part of the informed consent process (see Section 16.2).

Copies of any subject source documents that are provided to the sponsor must have certain personally identifiable information removed (ie, subject name, address, and other identifier fields not collected on the subject's eCRF).

### **16.4 Publication, Disclosure, and Clinical Trial Registration Policy**

#### **16.4.1 Publication and Disclosure**

The investigator is obliged to provide the sponsor with complete test results and all data derived by the investigator from the study. During and after the study, only the sponsor may make study information available to other study investigators or to regulatory agencies, except as required by law or regulation. Except as otherwise allowable in the clinical study site agreement, any public disclosure (including publicly accessible websites) related to the protocol or study results, other than study recruitment materials and/or advertisements, is the sole responsibility of the sponsor.

The sponsor may publish any data and information from the study (including data and information generated by the investigator) without the consent of the investigator. Manuscript authorship for any peer-reviewed publication will appropriately reflect contributions to the production and review of the document. All publications and presentations must be prepared in accordance with this section and the Clinical Study Site Agreement. In the event of any discrepancy between the protocol and the Clinical Study Site Agreement, the Clinical Study Site Agreement will prevail.

#### **16.4.2 Clinical Trial Registration**

In order to ensure that information on clinical trials reaches the public in a timely manner and to comply with applicable laws, regulations and guidance, Takeda will, at a minimum register interventional clinical trials it sponsors anywhere in the world on ClinicalTrials.gov or other publicly accessible websites before start of study, as defined in Takeda Policy/Standard. Takeda contact information, along with investigator's city,-country, and recruiting status will be registered and available for public viewing.

For some registries, Takeda will assist callers in locating trial sites closest to their homes by providing the investigator name, address, and phone number to the callers requesting trial information. Once subjects receive investigator contact information, they may call the site requesting enrollment into the trial. The investigative sites are encouraged to handle the trial inquiries according to their established subject screening process. If the caller asks additional questions beyond the topic of trial enrollment, they should be referred to the sponsor.

Any investigator who objects to Takeda providing this information to callers must provide Takeda with a written notice requesting that their information not be listed on the registry site.

#### **16.4.3 Clinical Trial Results Disclosure**

Takeda will post the results of clinical trials on ClinicalTrials.gov or other publicly accessible websites, as required by Takeda Policy/Standard, applicable laws and/or regulations.

### **16.5 Insurance and Compensation for Injury**

Each subject in the study must be insured in accordance with the regulations applicable to the site where the subject is participating. If a local underwriter is required, then the sponsor or sponsor's designee will obtain clinical study insurance against the risk of injury to clinical study subjects. Refer to the Clinical Study Site Agreement regarding the sponsor's policy on subject compensation and treatment for injury. If the investigator has questions regarding this policy, he or she should contact the sponsor or sponsor's designee.

## Appendix A Schedule of Events

**Table A Schedule of Events**

	Screening Period												Treatment Period							Safety Follow-up	Long-term Follow-up	
	Screening		Enroll- ment	Cycle 1						Cycle 2						Cycle 3 and Subsequent Cycles						
	-28 to 0	-14 to 0		-7 to 0	1	2	3	4	8	11	15	1	2	4	8	15	15 to 21 j	1	15	15 to 21 j		
Basis Date: Number of Days Starting on Day 1 of Each Cycle	-28 to 0	-14 to 0	-7 to 0	1	2	3	4	8	11	15		1	2	4	8	15	15 to 21 j	1	15	15 to 21 j	Day 30 after final dose o	Every 12 weeks
Visit Window								±1D				±1D	-1D to +3D		±3D	±3D		-1D to +3D	±3D		±7D	±14D
Informed consent	x																					
Enrollment a			x																			
Demographics	x																					
Medical history	x																					
Brentuximab vedotin administration b			x									x b						x b				
ECOG performance status c	x			x				x			x	x		x	x		x	x		x		
Height	x																					
Weight	x		x									x s					x s			x		
Vital signs d	x		x			x		x		x	x		x	x		x	x		x		x	
12-lead ECG	x		x i									x s					x s			x		
Hematology	x		x	x		x	x		x	x	x s	x	x	x	x	x s	x	x	x		x	
Chemistry A e	x		x			x		x		x s		x	x		x s	x	x s	x	x	x		
Chemistry B f	x																			x		
Coagulation	x		x						x	x s						x s			x			
Viral test	x																					
Urinalysis	x									x s					x s			x		x		
Pregnancy test	x																			x		
Concomitant medications/ procedures																						
AEs	SAE																					
CT scan	x												x			x l	x p	x q				
PET scan	x															x m	(x m )					
B symptom assessment	x			x					x			x			x		x p					

CONFIDENTIAL

	Screening Period												Treatment Period						Safety Follow-up	Long-term Follow-up	
	Screening		Enroll- ment	Cycle 1						Cycle 2						Cycle 3 and Subsequent Cycles					
	-28 to 0	-14 to 0		-7 to 0	1	2	3	4	8	11	15	1	2	4	8	15	15 to 21 j	1	15	15 to 21 j	
Basis Date: Number of Days Starting on Day 1 of Each Cycle	-28 to 0	-14 to 0	-7 to 0	1	2	3	4	8	11	15	1	2	4	8	15	15 to 21 j	1	15	15 to 21 j	Day 30 after final dose o	Every 12 weeks
Visit Window								$\pm 1D$			$\pm 1D$	$-1D$ to $+3D$			$\pm 3D$	$\pm 3D$		$-1D$ to $+3D$	$\pm 3D$	$\pm 7D$	$\pm 14D$
Bone marrow aspirate or biopsy	x h															x n			x n	(x n )	
PK g			x	x	x	x	x	x	x	x	x	x	x	x	x	x k			x		
Immunogenicity g			x								x					x k			x		
Survival follow-up																				x r	

CT= computed tomography, ECOG PS=Eastern Cooperative Oncology Group performance status, ECG=electrocardiogram, IWRS=interactive web response system, PET=positron emission tomography, PK=pharmacokinetics, SAE=serious adverse events.

Tests and procedures should be performed on schedule, but occasional changes may be allowed ( $\pm 3$  days) for holidays, vacations, and other administrative reasons. If the study schedule is shifted, assessments must be shifted to ensure collection of assessments is completed prior to dosing.

**X**=Within 3 days before the first dose. Screening tests within 3 days before the study dose on Day 1 of Cycle 1 may be substituted for testing on Day 1 of Cycle 1.

(a) The investigator or investigator's designee will access the IWRS at the screening visit to obtain a unique subject identification number. A subject is considered to be eligible to enter the enrollment visit when eligibility criteria are met. The subject identification numbers will be used consistently throughout the entire study and must not be changed.

(b) The start of the next cycle may be delayed for up to 3 weeks (up to 6 weeks from the current administration of brentuximab vedotin) if additional time is required for the patient to recover from study treatment-associated toxicity experienced during the current cycle. Delays of greater than 3 weeks (after Day 22) are prohibited without approval from the sponsor.

(c) Assessments on Day 1 of each cycle must be administered before dose of the study treatment.

(d) On Day 1 of Cycles 1 and 2, vital signs must be measured and recorded at the following times: predose; 15 ( $\pm 5$ ) minutes, and 30 ( $\pm 5$ ) minutes after the start of infusion; and upon completion of the infusion ( $\pm 10$  minutes). On Day 1 of Cycle 3 and subsequent cycles, vital signs must be measured and recorded at the following times: before the start of infusion and upon completion of the infusion (-5 to +10 minutes).

(e) Samples of glucose must be taken under fasting conditions (at least 4 hours after a meal) at screening and on Day 1 of Cycle 1. At other time points, although fasting levels (at least 4 hours after a meal) should be measured as a rule, nonfasting levels are also permitted; if a nonfasting level is measured, the meal times must be recorded on the source document.

(f) Samples of total cholesterol and triglycerides must be taken under fasting conditions (at least 4 hours after a meal) at screening. At other time points, although fasting levels (at least 4 hours after a meal) should be measured as a rule, nonfasting levels are also permitted; if a nonfasting level is measured, the meal times must be recorded on the source document.

(g) See Table B for details regarding PK and immunogenicity draws and windows. Immunogenicity samples must be taken before dosing.

(h) In patients with a positive bone marrow aspirate or biopsy following the most recent treatment of malignant tumor, bone marrow aspirate or biopsy do not need to be repeated.

(i) ECG on Day 1 of Cycle 1 within 3 days before study treatment and after completion of the infusion (+2 hours).

(j) On Days 15-21 after study drug dose of each cycle and before study drug dose of the next cycle.

(k) Sampling for PK and immunogenicity will be taken every 2 cycles after Cycle 3.

(l) CT scan will be performed every 3 cycles after Cycle 4 (Cycles 4, 7, 10, 13 and 16). It does not need to be performed at Cycle 3.

(m) PET scan will be performed at Cycles 4 and 7. No additional PET scanning is required beyond Cycle 7 unless clinically indicated.

(n) For patients with bone marrow involvement at Baseline, bone marrow aspirate or biopsy is required to confirm the CR status. Bone marrow aspirate or biopsy samples will be collected within 2 weeks after CT scans. Further bone marrow assessments are not required after bone marrow aspirate or biopsy becomes negative.

- (o) Safety follow-up assessments should be performed before initiation of subsequent antineoplastic therapy.
- (p) If possible, CT scans and B symptom assessments should be performed if not done within the previous 6 weeks.
- (q) Patients who discontinue study treatment with SD or better will be followed for PFS until disease progression, death, withdrawal of consent, or initiation of a new treatment, whichever occurs first. A CT scan will be performed every 12 weeks ( $\pm 14$  days) for the first 12 months and at 18 months after EOT.
- (r) Patients will be followed for OS every 12 weeks ( $\pm 14$  days) until death, withdrawal of consent, or study closure, whichever occurs first.
- (s) The testing on Day 1 is to be performed within 1 day before study treatment.

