## **7.0 STUDY DESIGN**

### **7.1 Overview of Study Design**

This is a single-arm, open-label, multicenter, phase 2 study designed to evaluate the efficacy, safety, and PK of brentuximab vedotin as a single agent in Chinese patients with relapsed/refractory CD30+ HL or sALCL. Brentuximab vedotin will be administered as a single, 1.8 mg/kg IV infusion on Day 1 of each 3-week cycle.

Patients will receive a maximum of 16 cycles if they do not meet the criteria for removal from the study. Patients will be assessed for overall response using the Revised Response Criteria for Malignant Lymphoma [1]. Dedicated computed tomography (CT) scans (neck, chest, abdomen, and pelvis) will be performed at Baseline and at Cycles 2, 4, 7, 10, 13, and 16, and positron emission tomography (PET) scans will be performed at Baseline and at Cycles 4 and 7. No additional PET scanning is required beyond Cycle 7 unless clinically indicated. B symptoms will be assessed at Baseline and on Day 1 of each cycle.

Patients may continue on study treatment until the sooner of disease progression, unacceptable toxicity, or completion of 16 cycles. Patients, including those who discontinue study treatment for any reason other than withdrawal of consent, will have safety follow-up assessments through 30 days after the last dose of study drug (end of treatment [EOT]). Patients who discontinue study treatment with stable disease (SD) or better will be followed for PFS until disease progression, death, withdrawal of consent, or initiation of a new treatment, whichever occurs first. A CT scan will be performed every 12 weeks for the first 12 months and at 18 months after EOT. Patients will be followed for OS every 12 weeks until death, withdrawal of consent, or study closure, whichever occurs first. All patients will have the opportunity to be followed for 18 months after EOT. The study will be closed when all patients enrolled have completed the required follow-up.

Toxicity will be evaluated according to the National Cancer Institute Common Terminology Criteria for Adverse Events (NCI CTCAE), version 4.03, effective 14 June 2010 [2]. Laboratory values, vital signs, and electrocardiograms (ECGs) will be obtained to evaluate the safety and tolerability of brentuximab vedotin. Serial blood samples for determination of the serum/plasma concentration and immunogenicity of brentuximab vedotin will be obtained at prespecified time points as described in Table B in [Appendix A](#).

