### **10.3.14 Disease Assessment**

Tumor response will be evaluated according to the Revised Response Criteria for Malignant Lymphoma [\[1\]](#).

All imaging will be performed with contrast, except for subjects in whom contrast imaging is difficult because of hypersensitivity to contrast medium, bronchial asthma, renal impairment, or other conditions.

Measurable lesions are those that meet all the following criteria:

- Lymph nodes diagnosed as lymphoma lesions, or nodular masses involving extranodal organs on CT imaging.
- Lesions that can be accurately measured in 2 perpendicular directions on CT cross-sectional images.
- Lesions with longest diameter  $\geq 1.5$  cm on CT cross-sectional images.
- FDG-PET positive lesions.

As many as 6 target lesions will be selected among the measurable lesions, whether nodal or extranodal, in order of decreasing longest diameter on CT cross-sectional images.

B symptoms will be assessed at prespecified time points as described in the Schedule of Events ([Appendix A](#)).

Bone marrow aspirate or biopsy will be performed within 2 weeks before the first dose of brentuximab vedotin (it is not necessary to repeat these procedures in patients with a positive bone marrow aspirate or biopsy performed after the most recent antineoplastic therapy). For patients with bone marrow involvement at Baseline, bone marrow aspirate or biopsy is required to confirm the CR status. Bone marrow aspirate or biopsy samples will be collected within 2 weeks after CT scans. Further bone marrow assessments are not required after bone marrow aspirate or biopsy becomes negative.

Timing of CT scans will be as follows:

- Screening period: Days -28 to 0.
- Cycles 2, 4, 7, 10, 13, and 16: Days 15 through 21 (before study treatment in the next cycle).

Subjects who discontinue study treatment or assessments for the reasons stated in Section 10.6 other than progressive disease (PD) and have not undergone assessment within the past 6 weeks should have tumor response assessed during the safety follow-up whenever possible.

Subjects who discontinue study treatment for any reason other than PD will have CT scans every 12 weeks ( $\pm$ 14 days) for the first 12 months and at 18 months after EOT until disease progression, death, withdrawal of consent, or initiation of a new treatment, whichever occurs first.

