## **10.9 Long-term Follow-up Assessments**

Patients who discontinue study treatment with SD or better will be followed for PFS until disease progression, death, withdrawal of consent, or initiation of a new treatment, whichever occurs first. A CT scan will be performed every 12 weeks ( $\pm 14$  days) for the first 12 months and at 18 months after the EOT. Patients will be followed for OS every 12 weeks ( $\pm 14$  days) until death, withdrawal of consent, or study closure, whichever occurs first. Survival information may be collected by methods including, but not limited to, telephone, e-mail, or mail. Patients will be followed until all patients have had the opportunity to be followed for 18 months after EOT. The study will be closed when all patients enrolled have completed the required follow-up.

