#### 7.5 Medical History and Concurrent Medical Conditions

A complete medical history will be compiled for each patient during the screening period prior to the first dose of brentuximab vedotin. General medical history of all patients will be presented in a by-patient listing in reported terms.

Concurrent medical conditions that will be assessed include B symptoms (persistent fever, drenching night sweats, and unexplained weight loss >10%) and clinical evaluations of palpable liver and spleen. These assessments will be presented over time in by-patient listings.

B symptom resolution rate is defined as the proportion of patients with lymphoma-related B symptom(s) at baseline who achieve resolution of all B symptoms at any time during the treatment period. For patients with any B symptom at Baseline, B symptom resolution rate and the 95% exact CI will be summarized.

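### The 6-week condition at safety follow-up switches off the B-symptom check whenever the schedule is kept, and read literally lets a baseline CT replace the only scheduled post-dose CT by EOT after a single dose

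*Protocol*

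**What the plan says.** - **B-symptom schedule.** Protocol Section 7.1: "B symptoms will be assessed at Baseline and on Day 1 of each cycle". Day 1 is the dosing day (Section 9.1).
- **Safety follow-up.** Table A places it at "Day 30 after final dose", with a window of 7 days either side.
- **6-week condition.** Footnote (p) to Table A, attached to both the CT and the B-symptom mark at that visit: "If possible, CT scans and B symptom assessments should be performed if not done within the previous 6 weeks". It does not say that the earlier assessment must follow the first dose.
- **Body text.** Section 10.3.14 covers patients who stop for a reason other than PD and "have not undergone assessment within the past 6 weeks should have tumor response assessed during the safety follow-up whenever possible". It does not mention B symptoms.
- **CT schedule.** Baseline: "Screening period: Days -28 to 0". On treatment: "Cycles 2, 4, 7, 10, 13, and 16: Days 15 through 21 (before study treatment in the next cycle". No CT is scheduled in Cycle 1.
- **Later CTs.** Section 10.3.14 gives 12-weekly CTs after any stop not due to PD. Section 10.9 is narrower: "Patients who discontinue study treatment with SD or better will be followed for PFS until disease progression". Section 7.1 and footnote (q) carry the same restriction.
- **Endpoints.** ORR counts CR or PR reached by EOT (Section 14.1.3). SAP 7.5 defines B-symptom resolution among patients symptomatic at baseline "who achieve resolution of all B symptoms at any time during the treatment period". SAP 7.8.2 censors PFS at the day of first dose when there is no tumor evaluation after that dose.

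**The concern.** A condition meant to avoid duplicate assessments does something else for B symptoms. They are checked at every dose and the visit is tied to the last dose, so the condition cancels the check that the table marks. A patient who stops after Cycle 1 may then have only the screening check and the one on dosing day. If symptomatic at baseline, that patient stays in the denominator of a named secondary endpoint with no required opportunity to be recorded as resolved. SAP 7.5 adds to this: it counts resolution in the treatment period, and Table A heads safety follow-up as a separate column, so even a voluntary check at that visit might not count.

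For CT, the same patient has no scheduled scan between the first dose and safety follow-up. If a recent baseline scan satisfies the condition, no scheduled tumor assessment after dosing falls before the ORR cut-off. The patient stays in the safety/mITT set without a documented response. Such patients are early stoppers, so the missing data are unlikely to be random.

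**Working it through.** The plan gives no figure for this point. It is a matter of counting days from the documents' own windows.

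**Inputs.** Condition: 6 × 7 = 42 days (footnote (p)). Safety visit: 30 − 7 = 23 to 30 + 7 = 37 days after the last dose (Table A). Last scheduled B-symptom check: day of the last dose (Sections 7.1 and 9.1). Baseline CT: 0 to 28 days before the first dose; first post-dose CT: Cycle 2, Days 15 to 21 (Section 10.3.14). Tolerances in the notes to Table A: 3 days for administrative shifts, and screening tests up to 3 days before the first dose may stand in for Cycle 1 Day 1.

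**Step 1, B symptoms.** Gap = visit day − day of last dose = 23 to 37 days. The check is required only if the gap exceeds 42.
- Schedule kept: at most 37, not triggered.
- One tolerance used: 37 + 3 = 40, not triggered.
- Both tolerances used (possible only after a single dose): 37 + 3 + 3 = 43, triggered.
- A missed Day 1 check or a visit outside its window could also trigger it.

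**Step 2, CT after a single dose.** A baseline CT taken *b* days before the dose excuses the scan at visit day *d* if *b* + *d* ≤ 42, so *b* ≤ 42 − *d*.

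| Visit day *d* | Largest excusing *b* |
|---|---|
| 23 | 19 |
| 30 | 12 |
| 37 | 5 |

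Over all allowed whole-day pairs (15 visit days × 29 CT days = 435), the condition is met in 20 + 19 + … + 6 = 195, or 45%. This counts combinations and is not a probability. A baseline CT 20 to 28 days before the dose never excuses the scan.

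**Step 3, when the next CT would come.** Under Section 10.3.14 the first long-term CT is at 84 ± 14 days. Counted from the last dose, that is days 70 to 98. Counted from the safety visit, it is days 23 + 70 = 93 to 37 + 98 = 135. Either way it comes after the safety visit. Under Section 10.9 a patient with no response category has no clear entitlement to it.

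**Step 4, size per patient.** One patient is 1/22 = 4.5 points of HL ORR or 1/8 = 12.5 points of sALCL ORR. If one third have baseline B symptoms (assumption: about 7 HL, 2 to 3 sALCL), one unassessed patient is about 1/7 = 14 points of the HL resolution rate, or 1/3 to 1/2 = 33 to 50 points of the sALCL rate.

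For scale, the plan's probabilities of at least 9 of 22 HL responses at a true rate of 65%, and at least 5 of 8 sALCL responses at 80%, reproduce by exact binomial as 99.4% and 94.4% (plan: above 99% and above 94%). If one patient per cohort is unassessed and counted as a non-responder (assumption), they become P(≥9 of 21) = 98.9% and P(≥5 of 7) = 85.2%.

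**Step 5, how many patients.** The documents give no rate of stopping after one dose. Taking 0 to 2 of 30 (assumption) and one third with B symptoms gives 0 to 2 × 1/3 = 0 to 0.67 patients for the B-symptom part. The CT part affects only those of the 0 to 2 whose baseline CT falls inside the step 2 limits.

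**The case against.** The strongest reply is that the protocol already covers most of this. Section 10.3.14 asks for tumor response to be assessed, and a baseline scan is not a response assessment, so the body text can be read as requiring the CT that footnote (p) excuses. It also gives 12-weekly CTs after any stop not due to PD, and imaging when symptoms suggest PD. Section 10.7 asks for final assessments before other therapy when possible. Footnote (p) sets a minimum and forbids nothing. Resolution counts at any time, so a patient with two or more cycles already has a check after dosing. Non-evaluable patients may be replaced (Section 10.6), no formal test is made on ORR (SAP 7.8.1), and counting an unassessed patient as a non-responder is conservative.

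Much of this stands, and it rules out several stronger readings that a reader might infer:
- *The B-symptom check can never occur.* Stacked tolerances, a missed Day 1 check or a late visit can trigger it. Section 9.2 allows the next cycle to be held until 6 weeks after the last dose, so a patient who then stops may have a late visit.
- *The excused CT is the only post-dose scan, so PFS is censored at first dose.* That follows only if the narrower rule in Sections 7.1, 10.9 and footnote (q) prevails, or if death, withdrawal or new treatment comes before the first long-term CT.
- *One-dose patients have no on-drug data.* They have vital signs including temperature, ECOG status and laboratory tests on Days 8 and 15, these and weight at safety follow-up, and adverse events through 30 days.

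One uncertainty remains. The B-symptom row of Table A, as extracted, carries six marks where the text of Section 7.1 plus safety follow-up needs five, and the column of the extra mark cannot be determined. If it falls after dosing in Cycle 1, the one-dose consequence weakens. Footnote (p) would then be even less likely to be triggered.

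The reply does not remove three things: a marked assessment that its own footnote cancels, a footnote and a body section that differ on what excuses the CT, and two incompatible rules on who has follow-up CTs. Replacement is discretionary and does not take a dosed patient with measurable lesions out of the safety/mITT set.

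**Conclusion.** The point holds in a limited form. When the schedule is kept, the last B-symptom check is 23 to 37 days before safety follow-up and the 42-day condition is not met, so the marked assessment is not required. A patient with baseline B symptoms who stops after one dose may therefore have no required check after dosing, subject to the unplaced mark in Table A, while remaining in the denominator. Read literally, footnote (p) also lets a baseline CT up to 19, 12 or 5 days before a single dose excuse the only scheduled post-dose CT by EOT. What is exposed there is ORR and CR rate. The PFS consequence depends on which follow-up rule is applied, and that contradiction needs resolving in any case.

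The effect per patient is visible in cohorts of 22 and 8, but few patients are likely to be affected (assumption: 0 to 2 of 30) and the efficacy analysis is descriptive. This is a low-priority but cheap correction.

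**What to change.** 1. **Table A:** remove the 6-week condition for B symptoms, so that they are assessed at safety follow-up in all patients who attend.
2. **SAP 7.5:** count resolution from the first dose through the safety follow-up visit. An extra assessment can only add resolutions, so fix this before database lock.
3. **Footnote (p) and Section 10.3.14:** state in both places that only a CT taken after the first dose, within the 6 weeks, excuses the scan at safety follow-up.
4. **Sections 7.1, 10.9 and footnote (q):** reconcile with Section 10.3.14 on who has follow-up CTs, and say explicitly what applies to a patient with no response category.

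The cost is a few questions at an existing visit, at most one CT in a rare one-dose patient, and wording changes in the protocol and SAP.
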